2. LAY SUMMARY

2.1. Background

Pleural infection is a common and serious complication of infection in the lung (pneumonia), which results in a collection of fluid between the chest wall and the lung. It affects more than 65,000 patients each year in the United States (US) and the United Kingdom (UK), and in the UK there are 40 new cases per day. The disease is fatal in 20% of people, and patients stay in hospital for an average of 13 days for treatment. The cost of treatment in the NHS is approximately £4000 per patient, equating to £58 million per year.

Standard treatment for pleural infection includes antibiotics and drainage of the fluid through a tube inserted between the ribs (chest drain). When patients do not respond to initial treatment, surgery is sometimes required. Alternatively, medications can be given through the chest drain which clears out the infected material (called Intrapleural Enzyme Therapy or IET). This treatment has been shown to reduce hospital stays and the need for surgery. Surgery is an effective treatment, but it has several side effects and is not an option for very unwell patients and the elderly, where the death rate is 40%.

Being able to predict which patients are most vulnerable to a bad outcome from a pleural infection (i.e. need surgery or die) at the start of treatment would be very valuable. This would help us to identify the sickest patients and offer the best treatment option as early as possible. Our group has developed a simple score (called RAPID) which uses information routinely collected in clinical care. We have proven that RAPID is reliable in identifying those at the highest risk of death and bad outcomes. What we do not know is whether we can use the RAPID score to inform treatment decisions and therefore benefit patients. To prove this, we need to conduct a large study. Before doing this, it is essential that we conduct a smaller pilot study to know such a large study would be possible, and that selecting the best treatment option according to RAPID score is acceptable to patients and doctors.

2.2. Study design and methods:

This pilot study will recruit 30 patients who are in hospital with a confirmed pleural infection from 4 UK centres over an 8 to 10 month period. The patients will be randomised (assigned by computer) to the standard treatment pathway or treatment driven by the RAPID risk stratification score. We will follow patients for up to 3 months. We will measure whether this approach to treatment decisions is acceptable to patients and doctors and whether the study answers the key questions. This will help us know if a larger, definitive study is possible.

We will also interview around 12 patients who are willing to be part of the study, and some who decide not to participate to understand what is important to them when treating this disease and their reasons for taking part or not. Additionally, we will interview 6 clinicians to assess their views and the acceptability of the study and to explore any barriers to participation. This will help us understand what should be measured in a larger study to best improve patient care.

We will collect pairs of pleural fluid and blood from all RAPTOR-f participants to measure the biomarkers and assess for microbiology alongside the septations score on the ultrasound scan to evaluate whether rising levels of these biomarkers will predict treatment failure for patients with pleural infection.

The biomarkers include suPAR (Soluble Urokinase Plasminogen Activator Receptor), PAI-1 (Plasminogen-Activator Inhibitor-1), NE (Neutrophil Elastase) and cytokines interleukins (IL) 1 and 2 on both blood and the pleural fluid.

3. SYNOPSIS

Study Title	RAPTOR – RAPID driven Treatment of Pleural Infection (feasibility study)			
Internal ref. no. / short title	RAPTOR -f			
Study registration	25/WA/0161	25/WA/0161		
Sponsor	University of Oxford Research Governance, Ethics and Assurance Team [name] [contact] [contact]			
Funder		Health and Care Research, Research on number NIHR207229	for Patient Benefit	
Study Design	Feasibility study			
Study Participants	 Adults with confirmed pleural infection requiring admission to hospital with: 1. A clinical presentation compatible with pleural infection or infective illness. 2. A pleural collection on radiology (CXR, ultrasound or CT) with a chest drain in situ or planned 3. Pleural fluid features diagnostic of infection which is either: A. purulent or B. gram positive or C. culture positive (pleural fluid or biopsy) or D. acidic with a pH<7.2 or E. low pleural fluid glucose <4.4 mmol/L or 72mg/dL(non-diabetic) or LDH ≥ 900 iu/L OR F. (non-fluid criteria) – CT findings suggestive of pleural infection (pleural enhancement) or pleural fluid septations on thoracic ultrasound 			
Sample Size	30 participants randomised (15 in each arm) from 3 to 4 centres		centres	
Planned Study Period	01/06/2025 - 01/03/2027			
Planned Recruitment period	10 months		_	
	Objectives	Outcome Measures	Timepoint(s)	
Primary	To assess the feasibility of recruitment, data collection and acceptability of the	 30 patients randomised 1:1 between RAPID driven treatment versus standard treatment. Recruitment and 	1. At recruitment completion	

			1
	participants and of Healthcare professionals of randomisation.	retention rate, the proportion of participants screened who consented to be randomised and who consented to be interviewed. Data completeness/availability and participant completion.	
		2. To conduct semistructured interviews with a proportion of the randomised participants and healthcare professionals	2. 4 to 6 weeks post hospital discharge
		3. The primary outcome will be defined as successful if ≥50% of the eligible patients are willing to be randomised and ≥ 50% of the healthcare provisional and participant agreed to take part into the interviews	3. At recruitment completion
Secondary	1. Length of hospital stay strategies.	1. Review completeness of data regarding the time of the participants staying in hospital over 3 months from randomisation until discharge.	1. From time of admission to hospital discharge
	2. Mortality rate over 3 months (all cause)	2. Proportion of participants who died (all cause) over 3 months post randomisation.	2. Until the end of the study
	3. Need for IET	3. Proportion of participants who required IET post randomisation	3. From time of admission until discharge
	4. Need for surgery	4. Proportion of participants who required surgery post randomisation	4. From time of admission until discharge

5. Medical	5. Proportion of participants who	5. From time of
treatment failure	did not respond to medical treatment (pleural fluid drainage + IET) and required surgery post randomisation.	admission until discharge
6. Need for repeat intervention and admission	6. Number of participants who need further pleural procedure e.g chest drain insertion or therapeutic thoracocentesis and proportion of the participant who required re admission to hospital.	6. Until the end of the study
7. Duration of antibiotics	7. Review completeness of data regarding the use of antibiotics from start date of antibiotics to date that has been stopped.	7. From day of starting antibiotics up to 6 weeks post discharge
8. Time to complete recovery and return to normal function	8. SF36 measurements	8. At 4 and 12 weeks post randomisation
9. Health related quality of life	9. EQ5D 5I questionnaire	9. At baseline, 2, 4 and 12 weeks post randomisation
10. Mean change and standard deviation in breathlessness and pain	10. Serial measurement of 100mm VAS score for breathlessness and pain	10. Post randomisation and until discharge from hospital
11. To assess feasibility of delivering the intervention arm (RAPID driven arm)	11. Record time of failure of medical treatment to surgery (VATS, thoracotomy) or time from ICD insertion to IET	11. End of the study
12. Healthcare utilisation	12. Number of pleural procedures and days in hospital post randomisation	12. During hospital stay

	13. To assess the pattern of computed tomography of the chest (CT chest) in pleural infection	13. Computed tomography of the chest to assess for consolidation	13. During hospital stay
	e.g., consolidation 14. Radiological changes following treatment	14. Chest x- Ray to assess for pleural thickening	14. At 12 weeks post randomisation
	15. To assess if levels of pleural fluid and blood biomarkers (suPAR, PAI-1, IL 1+2, and NET) will predict treatment failure	15. The proportion of participants with an elevated level of pleural fluid and blood biomarkers in serial samples taken on day 1 (randomisation day), 3 and 5(post - randomisation) who did not respond to medical treatment.	15. During hospital stay and while the chest drain in situ (optional).
Intervention(s)	In the intervention arm, following randomisation, a baseline RAPID score will		

Intervention(s)

In the intervention arm, following randomisation, a baseline RAPID score will be calculated (see Table 1). According to the score, participants will be allocated into two groups, as outlined below. The subsequent treatment will be determined by the calculated RAPID score.

Low RAPID score group:

- Admission for drainage Therapeutic aspirate or short-term chest tube insertion for 24 hours and subsequent tube removal if there are no features of sepsis syndrome or significant residual collections, see predefined treatment failure criteria below.
- Early discharge home within 24 to 48 hours of admission if they meet the proposed discharge criteria (see page 26) and they will be provided with a 24/7 contact number for the clinical study fellow if they have any concerns.
- Review in clinic within 3days +/- 2 days, if any features of medical treatment failure are present, they will be admitted to hospital and treated as a medium-high risk score group.

Medium – high RAPID score group:

- Admission for drainage Chest tube insertion
- Intrapleural instillation of recombinant human deoxyribonuclease (DNAse) 5mg BD (diluted in 30mls sterile water) and Recombinant human tissue plasminogen activator (tPA, Alteplase) 5-10mg BD (diluted in 30mls sterile water) intrapleural immediately after chest drain insertion if deemed safe and no contraindication e.g. no active bleeding or bleeding disorder.

	 Surgical referral at time of chest tube insertion for consideration of Video Assisted Thoracoscopic Surgery (VATS) or open surgery. 	
Comparator	Standard care and intergroup comparison in the RAPID driven arm.	
	The standard care involves admission to hospital, chest drain insertion and antibiotics as defined by recent British Thoracic Society guidelines 2023(1), if this fails in 3 to 5 days, patients will be referred to a thoracic surgeon for assessment for VATS or open surgery. Alternatively, IET may be considered if it is deemed safe and appropriate.	

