9.9. Subsequent Visits (Outpatient follow up)

Follow Up (applicable to both arms)

- 1. On discharge, all patients should be followed up in pleural clinic at day 14 and 28 +/- 3 days post discharge with assessments of blood parameters (CRP, liver and renal profile, FBC), chest x-ray and thoracic ultrasound as per standard NHS care.
- 2. A telemedicine review via phone will occur at 90 +_ 3 days post-discharge to collect longer-term outcomes.

3. *The total length of antibiotic treatment given* will be determined by local physicians and clinical response, but it is suggested to be at least 3 weeks total treatment (as per national standards).

Follow Up (Intervention arm only)

In the intervention arm, a clinical review will be arranged in 3 days +/- 2 days after discharge for low RAPID score group participants where bloods (CRP, full blood count, renal and liver profile), thoracic ultrasound and chest x ray will be conducted and the treatment failure criteria will be applied at the time of follow up, should any of these criteria full filled, the participant will be admitted to hospital and treated as intermediate to high score group.

Below is the summary of assessments in each outpatient visit which will be recorded into electronic CRF (REDCap).

Assessment	Day 3 +/-2 days follow up (Low RAPID score group only), post discharge	14 days +_ 3 days follow up	28 days +_ 3 days follow up	90 days +_ follow up (phone call)
Clinical assessment (review symptoms and clinical examination)	Yes	Yes	Yes	NA
Thoracic ultrasound	Yes (part of the research)	Yes (standard care)	Yes (standard care)	NA
Blood (FBC, U and Es, liver function and CRP) – standard NHS care	Yes	Yes	Yes	NA
Chest x ray	Yes	Yes	Yes	Yes (remote review)
Readmissions to hospital	Yes	Yes	Yes	Yes (remote review)
Requirement for further chest drain insertion	Yes	Yes	Yes	Yes (remote review)
Requirement for surgery	Yes	Yes	Yes	Yes (remote review)
Mortality rate	Yes	Yes	Yes	Yes (remote review)
Health related quality of life using EQ-5D-5L	NA	Yes	Yes	Yes (remote review)
Assessment of functional ability (SF36)	Na	Yes	Yes	Yes (remote review)
VAS score pain and breathlessness	NA	Yes	NA	Yes (remote review)

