13.1. Description of the Statistical Methods

13.1.1. Analysis of the RAPTOR f feasibility study:

Feasibility parameters will be measured and reported, and include:

- Recruitment proportion (number of randomised patients divided by number of eligible patients)
- Randomisation acceptance rate (proportion of patients who are willing to be randomised over those eligible)
- Retention (number of participants who complete intended treatment, number of participants who complete intended follow up)

These will be reported and used to assess whether or not a definitive trial is feasible. Descriptive statistics will be used to describe the demographic characteristics between the two groups. For categorical variables, numbers (and proportions) will be reported for each treatment group and overall. For continuous variables, means and standard deviations (or medians in the interquartile range) will be reported for each treatment group and overall. As this feasibility study is not powered to draw definitive conclusions, comparisons between the two arms for clinical outcomes will be reported using descriptive statistics only. No statistical tests will be carried out. These will be based on multivariable linear (for continuous outcomes) or logistic (for binary outcomes) regression with adjustment for stratification factors and important prognostic factors and will be reported as adjusted differences in means (for continuous outcomes) or proportions (for binary outcomes). Treatment comparisons will be reported for the intention-to-treat population (all randomised participants will be analysed according to their allocated treatment group irrespective of which treatment they actually receive) as treatment effects together with 95% confidence intervals for the two main comparisons: (1) Standard care vs overall RAPID driven treatment (2) Low RAPID driven treatment arm vs moderate to high RAPID driven treatment arm. Compliance to the interventions will be reported.

To establish the feasibility of collecting accurate long-term outcomes in randomised participants, we will present the completeness of the outcomes across the duration of the trial. The outcome measures collected in this study will be used to inform the sample size for the future definitive large-scale phase III RCT if it is feasible to be undertaken.

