Adverse events and serious adverse events will be reported by each arm in the intervention group on the safety population only (all patients who received the allocated treatment).

It is anticipated that STATA (StataCorp LP) or other appropriate validated statistical software will be used for analysis.

13.1.2. Analysis of the embedded qualitative:

Interviews will be digitally audio-recorded, transcribed verbatim, and de-identified before being uploaded to data management software. The interview data will be analysed using Thematic Analysis. Audio-recordings will be listened to, and transcripts read and re-read for familiarisation, then opencoded to develop an initial code list. Codes will then be grouped into categories, and data explored to identify connections and to develop a descriptive account of the dataset as a whole. The analysis will

focus on the acceptability of study processes to patients, individual and group equipoise, and the patient experience of pleural infection and treatment.

For the RAPTOR-f study and embedded qualitative interviews, we will use robust progression criteria (see Table 1) to assess the feasibility of progression to a definitive phase III trial; green indicates all criteria are met, and if met, a larger study will be declared feasible. If one or more criteria are amber, this will result in mitigations including:

- o Review of qualitative data to identify barriers and potential mitigations
- o Discussion of recruitment to date and barriers with the study management group
- o Consideration of widening the recruited population and increasing centres

Table 1: Illustrate stop and go criteria for study progression, this will be applied for all centres, if any criteria are red, this will prompt major changes to the study or qualitative study design.

Criteria	Green	Amber	Red
Recruitment proportion (number eligible versus number randomised)	>50%	30% - 50%	< 30
Average monthly recruitment* (pts/centre/month)	≥1.0	0.5 – 0.9	< 0.5
Adherence to the allocated intervention group	≥90%	75% - 90%	< 75%
The proportion of key date completion (e.g Visual Analogue Score)	≥98%	75% - 97%	< 75%
Proportion completing study protocol (accounting for 10% expected attrition)	≥90%	75% - 90%	< 75%
Individual site recruitment (at 10 months)	≥10	5 – 9	< 5
Proportion completing clinicians' interview	>50 %	30% - 50%	< 30%
Proportion completing patients' interview	>50%	30% - 50%	< 30%

^{*} Once all centres have been greenlighted

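### The synopsis times retention, participant completion and data completeness at the end of recruitment, before later recruits can have finished their 90-day follow-up

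*Protocol*

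**What the plan says.** In the synopsis (section 3), primary outcome measure 1 lists recruitment together with "retention rate, the proportion of participants screened who consented to be randomised and who consented to be interviewed. Data completeness/availability and participant completion". The timepoint column gives the whole measure one entry: "1. At recruitment completion". Section 6 repeats the measures without timepoints, so the synopsis is the only place that times them.

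Section 13.1.1 includes in retention the "number of participants who complete intended follow up". Section 9.9 fixes the end of that follow-up: "A telemedicine review via phone will occur at 90 +_ 3 days post-discharge to collect longer-term outcomes". The synopsis also has a randomisation-based anchor for late follow-up, with the SF-36 due "At 4 and 12 weeks post randomisation".

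The progression table in section 13.1.2 has a row for the proportion completing the protocol, which allows for 10% attrition (green at 90% or more, red below 75%). Another row covers completion of key data (green at 98% or more). Neither row says when it is read.

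Four other places imply a later reading:
- Section 13.1.1 will present outcome completeness over the whole trial.
- Section 13.4 plans no interim analysis.
- Section 13.7 starts the final analysis only after database lock.
- Section 11 defines the end of study by, among other things, completed follow-up.

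**The concern.** A measure that needs about three months of follow-up after discharge cannot be read on the day the last participant is randomised. Someone following the synopsis must either count participants who are not yet due as not retained, which deflates the figure, or restrict it to early recruits, for which no rule is given. The protocol gives no way to choose between these. Section 13 says no separate analysis plan will be used, so the point is not left for another document to settle.

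The wording does not look like loose shorthand. The same synopsis column uses end-of-study labels for secondary outcomes 2, 6 and 11, so a later label was available. What is at stake is the reported primary measure and, if the progression table were read at the same moment, one of the criteria that decide whether a definitive trial is declared feasible.

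**Working it through.** **Inputs from the protocol**
- Target 30 randomised. Section 13.2 gives 3–4 centres, 10 months and 1 patient per centre per month; 3 × 10 × 1 = 30 reproduces the target.
- Recruitment period T: 8–10 months (section 9.1). At 30.4375 days per month this is 243.5 to 304.4 days.
- Last contact: 90 days after discharge (section 9.9), or 12 weeks = 84 days after randomisation (synopsis, SF-36).
- Mean hospital stay: 14 days (section 13.2). A discharge-based contact therefore falls about 90 + 14 = 104 days after randomisation.

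**Assumptions (not in the protocol)**
- Accrual is roughly even.
- The denominator is all randomised participants.
- Stay is counted from randomisation.

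**Formula.** With lag L from randomisation to last contact, the share not yet due when recruitment closes is L/T. The highest possible retention, with no drop-out, is 1 − L/T.

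| T | L (days) | Not yet due | Ceiling on retention |
|---|---|---|---|
| 10 months | 84 | 84/304.4 = 27.6% | 72.4% |
| 10 months | 90 | 90/304.4 = 29.6% | 70.4% |
| 10 months (base case) | 104 | 104/304.4 = 34.2% | 65.8% |
| 8 months | 84 | 84/243.5 = 34.5% | 65.5% |
| 8 months | 90 | 90/243.5 = 37.0% | 63.0% |
| 8 months | 104 | 104/243.5 = 42.7% | 57.3% |

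With 10% attrition the base-case ceiling becomes 0.9 × 65.8% = 59.2%.

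**Shorter stays in the low-risk group.** Section 13.2 expects half of the intervention arm, a quarter of all participants, to go home within 48 hours. Mean stay is then 0.75 × 14 + 0.25 × 2 = 11 days and L = 101. The share not yet due is 101/304.4 = 33.2% (10 months) or 101/243.5 = 41.5% (8 months), so the result hardly moves.

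**Recruitment length needed to leave red.** The ceiling reaches 75% when T = L/0.25. For L = 84 this is 336 days (11.0 months); for L = 104 it is 416 days (13.7 months). Both exceed the plan.

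**If accrual is random rather than even.** Leaving red needs at least 23 of 30, since 22/30 = 73.3%. The last participant enters at T and cannot be due, so at least 23 of the other 29 must be, each with probability 1 − L/T. For T = 10 months the binomial probability is 8.7% at L = 104 and 27% at L = 84. With 10% attrition these fall to 1.9% and 7.6%.

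**Data completeness.** Take the VAS at baseline, day 28 and day 90 (section 9.10), the last two counted from discharge after a 14-day stay. At 10 months the ceiling is [1 + (1 − 42/304.4) + (1 − 104/304.4)]/3 = (1 + 0.862 + 0.658)/3 = 84.0%. Other readings of the VAS schedule give up to about 87%. All are below the 98% green line because day-90 values do not yet exist.

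**After the change.** All 30 can be observed. With 10% attrition, expected completion is 27/30 = 90%, on the green threshold.

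**The case against.** The strongest reply is that the sponsor evidently intends a later reading. Completeness over the whole trial, no interim analysis, final analysis after lock and an end of study that requires completed follow-up all make an early retention read-out unlikely in practice. This stands, and it limits the harm. It does not make the synopsis timepoint right: no passage moves retention to the end of follow-up, and none limits the denominator to participants already due.

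A reader might infer that the completion criterion is bound to be red. The documents do not support that, for three reasons:
- The progression table states no reading time for the completion row, although its site-recruitment row carries a 10-month label and its monthly rate counts only from when all centres are open. That the synopsis timepoint governs the completion row is an inference.
- Even accrual is an assumption. Front-loaded accrual could lift the figure to amber; staggered site opening would lower it.
- Success under primary measure 3 rests on willingness to be randomised and agreement to interview. Retention plays no part in it.

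A reader might also extend the point to the interview criterion. That does not carry over as a percentage of the 30. Section 9.11 interviews a selected sample of up to 12 patients, including some who declined randomisation. Measure 3 concerns agreement rather than completion, and section 9.3 lists the interview information sheet among the papers given at consent.

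**Conclusion.** The synopsis timepoint is wrong as written for retention, participant completion and data completeness, and it conflicts with sections 11, 13.1.1, 13.4 and 13.7. With roughly even accrual over 8–10 months and all randomised participants as the denominator, about 28–43% would not have reached the last contact at recruitment completion (34% in the base case), capping apparent retention at about 57–72%.

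The effect on progression is conditional. If the completion row were read at that moment, red would be very likely in the base case with no drop-out (about 91% under random arrival), and less so at the shortest lag over 10 months (about 73%). The formal success rule is unaffected. This is a defect of timing and wording that should be corrected; it does not invalidate the design.

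**What to change.** Split the timepoint of primary outcome measure 1 in the synopsis:
- Keep recruitment completion for recruitment, acceptance and consent proportions.
- Read retention, participant completion and data completeness once the last randomised participant's day-90 window has closed and before database lock.
- State that same reading time under the progression table for the protocol-completion and key-data rows.

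The cost is a few lines of text and a later read-out. With a 14-day stay, the last window closes 14 + 93 = 107 days, about 3.5 months, after the last randomisation, or about month 13.5 of a 10-month recruitment. The planned study period of 01/06/2025 to 01/03/2027 is 21 months, so it fits. No visits or data are added.

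In the same edit, reconcile when the interview information sheet is given (section 9 table footnote, 9.3 and 9.11) and whether interviews are timed from discharge or from recruitment (synopsis, section 9 table footnote and 9.11).

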9.6. Blinding and code-breaking

There is no blinding in this study, hence no un-blinding procedures or code-breaking are required.

9.7. Description of study intervention(s), comparators and study procedures (post-randomisation and inpatient period)

Intervention arm

In the intervention arm, treatment will be determined according to the calculated baseline RAPID score.

Patients with a higher RAPID score (and thus higher predicted mortality and morbidity (7,12)) will be triaged to more aggressive treatment early in the disease, and those with lower predicted mortality and morbidity will be treated less aggressively.

A. Low risk (RAPID score 0 to 2):

Patients will be treated as follows:

- 1. Pleural drainage: therapeutic pleural aspiration (drain to dryness) using a Rocket kit will be suggested as the initial treatment. If the patient has already had a chest tube inserted prior to randomisation (as randomisation can occur for 24 hours after drain insertion), then patients will be admitted for drainage for a proposed maximum of 24 to 48 hours, with the removal of the drain as soon as possible, provided there is no residual collection of pleural fluid on the chest-xray (CXR) or thoracic ultrasound or CT scan before drain removal. No specific size of drain is specified, and local practice should be followed.
- 2. **Broad spectrum antibiotics**: see below for the expected standard of care in both intervention groups concerning antibiotics, which are as per NHS standard care for pleural infection. Use of early oral antibiotics to promote discharge is recommended in this group.
- 3. **Review at 3 days +_ 2 days post-discharge** with bloods including full blood count, CRP (Creactive protein), liver and renal profile, ultrasound scan and chest x ray.
- 4. **Patient contact:** All patients will receive a 24-hour contact number (to the study fellow) who can be contacted should there be any concern or deterioration when at home which will prompt urgent review by the pleural service locally.

If at any point a patient is considered to have *failed treatment* on the basis of predefined criteria (see below), they will then be treated as per the intermediate/high-risk group below and will be admitted to hospital.

B. Intermediate + high-risk (RAPID score 3 to 7)

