 - b. A **serum CRP** (C-reactive protein) that fails to fall by more than or equal to 50% compared to the baseline value (from 48 hours after treatment).
 - c. Lack of significant response in the **peripheral blood white-cell count value** (from 48 hours after treatment) as judged by local investigators.

To ensure objective decision-making and patient safety we will suggest applying **objective discharge criteria** for both arms as the total length of hospital stay is a potentially important primary outcome in the large-scale trial is prove this approach is safe. Discharge will occur **only once all** of the following are met:

- a. Chest drain removed.
- b. No clinical features of sepsis syndrome.
- c. Significantly reduced inflammatory markers according to local physician review.
- d. Significant reduction in pleural fluid on radiology according to local physician review.
- e. Switched to oral antibiotics (at local physician's discretion).

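### Length of stay, IET, surgery and treatment failure are timed to end at discharge, which the intervention brings forward for low-RAPID patients, and other sections use longer windows

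*Protocol*

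**What the plan says.** **Outcome windows (Protocol, section 3, secondary outcomes, timepoint column).**
- Outcome 1, length of stay: "1. From time of admission to hospital discharge". The measure beside it reads "staying in hospital over 3 months from randomisation until discharge", so the two columns differ in start point and possibly in end point.
- Outcome 3, need for IET: "3. From time of admission until discharge".
- Outcome 4, need for surgery: "4. From time of admission until discharge".
- Outcome 5, medical treatment failure: again "admission until discharge".
- Outcome 12, pleural procedures and days in hospital: limited to the hospital stay.
- Outcome 6, repeat pleural procedure and readmission: runs to the end of the study.

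**Care of the low-RAPID group.** The synopsis plans "Early discharge home within 24 to 48 hours of admission", provided the discharge criteria are met. Section 9.7 says that if such a patient fails treatment, "they will then be treated as per the intermediate/high-risk group below and will be admitted to hospital".

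**Failure criteria (section 9.7).** They apply from randomisation to four weeks of follow-up in both arms. They are generally applied at about 72 hours after randomisation for standard care and medium-high RAPID, but at day 3 ± 2 after discharge for low RAPID.

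**Follow-up (section 9.9).** Readmission, further chest drain, surgery and death are recorded at days 14, 28 and 90 in both arms, and also at day 3 for low RAPID. The table has no row for IET or for days spent in hospital on readmission.

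**Use of the results.** Section 9.7 states that "the total length of hospital stay is a potentially important primary outcome in the large-scale trial". Section 13.1.1 reports treatment effects with 95% confidence intervals and uses the outcomes to inform the definitive sample size.

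**The concern.** An outcome window should not depend on the treatment being compared. Here its end point is discharge, and earlier discharge is what the intervention sets out to achieve in about half of its arm.

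For a low-RAPID patient the planned order is discharge, then failure check, then readmission and the medium-high pathway (IET, surgical referral) if the check is failed. If discharge means first discharge, outcomes 1, 3, 4, 5 and 12 close before the scheduled failure check. A standard-care patient is reviewed at 48 to 72 hours and, with an average stay of 14 days, will normally still be in hospital, so failure and escalation fall inside the window.

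For length of stay, surgery and treatment failure, the expected result is a picture too favourable to RAPID-driven care. For IET the direction is not simple, because IET is also protocol treatment for the RAPID 3 to 7 group.

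Both comparisons in section 13.1.1 (standard care against RAPID overall, and low against moderate-high RAPID) would set groups with unequal windows side by side. The resulting estimates are meant to inform the size of the next trial.

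**Working it through.** **1. The windows side by side**

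| Item | Where | Ends at |
|---|---|---|
| Outcomes 1, 3, 4, 5 | Section 3, timepoint column | Discharge (first or final not stated) |
| Outcome 12 | Section 3, timepoint column | Hospital stay |
| Outcomes 3, 4, 5, 12 | Sections 3 and 6, measure column | Post-randomisation, no end given |
| Outcome 1 | Sections 3 and 6, measure column | Over 3 months, yet also until discharge |
| Failure criteria | Section 9.7 | Four weeks of follow-up |
| Surgery, drain, readmission | Section 9.9 table | Day 90, both arms |
| IET, readmission days | Section 9.9 table | No row |
| IET, surgery, health utilisation | Section 9 schedule | Appears to be inpatient assessment only |

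Surgery after discharge is therefore collected but falls outside outcomes 4 and 5 as timed. IET on readmission and readmission bed-days have no stated collection point after discharge.

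**2. The plan's own sample size**

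Inputs from section 13.2: mean stay 14 days, SD 10, difference 4 days (8 days saved in the 50% at low risk: 0.5 × 8 = 4), 5% significance, 90% power, 1:1. Taking the test as two-sided:

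n per arm = 2 × (1.960 + 1.2816)² × 10² / 4² = 131.3, rounded up to 132; total 264. The stated figure reproduces.

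**3. What readmission days would do to the 4-day saving**

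Let f be the share of low-risk patients readmitted and D the days per readmission. The protocol gives neither for this group, so both are assumptions. With no readmissions in standard care and SD kept at 10:

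- Saving in total days = 4 − 0.5 × f × D
- Power at 132 per arm = Φ(saving / 1.231 − 1.960), where 1.231 = 10 × √(2/132)

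| f | D (days) | Saving (days) | Power at 264 | Total for 90% power |
|---|---|---|---|---|
| 10% | 7 | 4 − 0.35 = 3.65 | 84% | 316 |
| 20% | 10 | 4 − 1.00 = 3.00 | 68% | 468 |
| 20% | 13 | 4 − 1.30 = 2.70 | 59% | 578 |
| 30% | 14 | 4 − 2.10 = 1.90 | 34% | 1,166 |

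The 20% and 13 days borrow the overall medical failure rate and mean stay from section 5. They describe all patients, not low-risk readmissions.

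**4. Scale in this study**

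Half of 15 is about 7.5 low-risk patients in the RAPID arm. With f from 10% to 30%, that is 0.75 to 2.25 rescued patients, or 5 to 15 percentage points of the arm, outside a first-discharge window.

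**The case against.** A reader might infer that post-discharge events disappear from the RAPID arm altogether. The documents do not support that. Section 9.9 records readmission, further drains, surgery and death to day 90 in both arms, outcome 6 runs to the end of the study, and standard-care events after discharge are cut off too. The loss is differential, not confined to one arm, and its mechanism concerns only the low-RAPID half.

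Nor is it settled that the outcomes stop at first discharge. The measure column says post-randomisation, section 6 has no timepoint column, and discharge is never defined as first or final. That is fair, but an outcome that can be read two ways, with one reading tied to allocation, still needs fixing. Section 13 says there will be no separate SAP to resolve it.

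Two other strong readings fail. The bias cannot be said always to favour RAPID: the direction for IET is unclear, and early discharge is conditional on all the discharge criteria being met. The mismatch between admission and randomisation as the start of length of stay precedes allocation, so it creates no systematic difference between arms; it only needs aligning.

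Length of stay is called a potential primary outcome of the large trial, not the chosen one. Section 13.2 takes its SD from previous studies, so the power losses above are not shown to follow from the synopsis timepoints.

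The consequences within this study are also limited. These are secondary outcomes in 30 patients, no tests are planned, outcome 1 is worded as a completeness review, and none of the eight progression criteria uses them. The eCRF is not shown and may hold the missing fields. All of this stands and lowers the severity, but section 13.1.1 still reports effect estimates with intervals and carries the outcomes into planning.

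**Conclusion.** The point holds as a should-fix. As timed in the synopsis, outcomes 1, 3, 4, 5 and 12 end at discharge or cover only the hospital stay. If that means first discharge, they close before the low-RAPID group's scheduled failure check and any rescue. They also disagree with the four-week failure window and the day-90 follow-up. For length of stay, surgery and treatment failure, the expected distortion favours the RAPID arm.

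The decision on feasibility is not at risk. What is at risk is the descriptive comparison and any length-of-stay difference carried into the definitive trial. The size cannot be derived from the protocol, which gives no readmission rate or duration for low-risk patients. The assumed cases in the working put the saving at 1.9 to 3.65 days instead of 4. They are illustrations that rest on no standard-care readmissions and an unchanged SD, not forecasts.

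**What to change.** 1. Give outcomes 1, 3, 4, 5 and 12 one window, randomisation to day 90, the same in both arms and regardless of discharge.
2. Define length of stay as total hospital days from randomisation to day 90, including readmissions. Show deaths separately and keep the index stay as a supporting summary.
3. Make sure that IET given after discharge, and readmission and discharge dates, are recorded at the existing 14-, 28- and 90-day contacts.
4. Align the synopsis timepoints with section 6, the section 9 schedule, the failure-criteria window in section 9.7 and the follow-up table in section 9.9. Section 9.9 times the last call from discharge (90 ± 3 days), so for a patient discharged soon after randomisation an early call could fall up to three days short of day 90 from randomisation. State how that is handled.

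The cost is outcome wording and at most two extra eCRF items at contacts that already ask about readmission and surgery. Clinical management does not change. Readmission dates and IET may be hard to recover later if they are not collected at the time.
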